11.2. Planned Statistical Analysis

At the completion of the last study subject, the blinding will be broken and the aggregate results of the treatment and control arm will be compared.

The primary outcome measure is the change in monthly vertigo episodes. Per the AAO guidelines⁴, this has a numeric value of $X/Y \times 100$, where X is the average number of definitive spells per month after therapy, and Y is that rate prior to therapy. Categories A-F are designated, and the Chi-square/Fisher's Exact test will be used to compare the treatment and placebo groups.

[figure not shown]
Numeric Value	Class	Description
0	A	Complete control
1 to 40	B	Substantial control
41 to 80	C	Limited Control
81 to 120	D	Insignificant Control
> 120	E	Worsening of symptoms
	F	Secondary treatment initiated due to disability from vertigo

Secondary outcome measures are the average hearing threshold and word recognition score, which will be compared by repeated-measures ANOVA. Another secondary outcome measure is the patient Meniere's functional level before and after treatment (Appendix 2).

[figure not shown]

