3. CHARACTERISTICS OF THE RESEARCH POPULATION

3.1. Subject Characteristics

- a) **Number of Subjects:** We plan to enroll up to 40 subjects in order to accrue 15 randomized to the treatment arm of the study and 15 assigned to the placebo/control arm.
- b) **Gender and Age of Subjects:** Subjects 18 years of age and older will be included in the study and there will be no restriction on gender.
- c) **Racial and Ethnic Origin:** There will be no restriction based on race or ethnicity.

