5.1. Efficacy Assessments

Efficacy will be determined by comparing the frequency and severity of post-treatment Ménière's disease attacks with pretreatment patterns. Clinical response will be classified by AAO guidelines⁴: frequency of definitive vertigo episodes per month, average hearing threshold, word recognition score, and functional level.

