6. SUBJECT WITHDRAWALS

Subjects will be advised in the written informed consent forms that they have the right to withdraw from the study at any time without prejudice. Subjects will be withdrawn from the research without their consent by the investigator if they are non-compliant (miss scheduled study visits), or if the investigator determines that it is in the best interest of the subject. Also if the subject develops bilateral Ménière's disease during the study they will be withdrawn. There are no additional study activities requiring completion prior to subject withdrawal from the study. Subjects withdrawn from the study will not be replaced.

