11. DATA ANALYSIS AND MONITORING

11.1. Sample Size Determination

The pilot study^{2,3} showed that mastoid oscillation treatment was highly efficacious. Of 66 subjects that were treated, 22 (33.3%) achieved complete control, 30 (45.4%) achieved substantial control, 11 (16.7%) achieved limited control and three (4.5%) had insignificant control. A control group (N=30) with delayed start of treatment had just 2 subjects with improvement of symptoms (complete or substantial) during the wait period (6.6%).

For our sample size projection, we assume that the Mastoid Oscillation arm will have a 75% rate of achieving substantial or complete control, and 12% for the placebo group. With 15 subjects in each group, using Fisher's Exact test, the design has 95% statistical power with alpha of 0.012.

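### The 95% power stated in section 11.1 is not the power of its named test (82.8% two-sided, 86.8% one-sided at alpha 0.012), and section 11.2 should name that one test on A+B versus C-F, with its level and sidedness

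*Combined protocol and SAP*

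**What the plan says.** Section 11.1 gives the design assumption: "we assume that the Mastoid Oscillation arm will have a 75% rate of achieving substantial or complete control, and 12% for the placebo group". It then states that, with 15 subjects per group, "using Fisher's Exact test, the design has 95% statistical power with alpha of 0.012". It does not say whether the test is one-sided or two-sided, and it does not explain the value 0.012.

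Section 11.2 defines the outcome: "The primary outcome measure is the change in monthly vertigo episodes", expressed as the post-treatment rate over the pre-treatment rate times 100 and sorted into six classes. Complete control is class A and substantial control is class B. The comparison is described in one sentence: "Categories A-F are designated, and the Chi-square/Fisher's Exact test will be used to compare the treatment and placebo groups". Section 11.2 gives no grouping of the classes, no significance level, no sidedness and no rule for choosing between the two tests.

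**The concern.** There are two linked matters.

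First, 11.1 states every input to the power calculation except sidedness, so the claim can be checked directly. A power that is too high understates the chance that a treatment with the planned effect is declared ineffective.

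Second, 11.2 does not repeat the endpoint and test on which 11.1 sizes the trial. Read alone, it could mean an unordered comparison of six classes, or a two-group comparison by either of two tests. Those tests can give different answers with 15 per arm, so the plan should say before unblinding which one decides the trial.

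**Working it through.** **Inputs (section 11.1).** Response means class A or B. Rates are 75% (oscillation) and 12% (placebo), n = 15 per arm, Fisher's exact test, alpha 0.012. Claimed power: 95%. Sidedness is not given, so both were tried.

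**Formula.** Let A ~ Bin(15, 0.75) and B ~ Bin(15, 0.12) be the responder counts. Power is the sum over all 16 x 16 outcomes of P(A = a) x P(B = b), counting those with Fisher p <= 0.012. For each placebo count b, the test rejects once the active count reaches a minimum a*:

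| b | P(B = b) | a*, two-sided | P(A >= a*) | a*, one-sided | P(A >= a*) |
|---|---|---|---|---|---|
| 0 | 0.1470 | 7 | 0.9958 | 6 | 0.9992 |
| 1 | 0.3006 | 9 | 0.9434 | 8 | 0.9827 |
| 2 | 0.2870 | 10 | 0.8516 | 9 | 0.9434 |
| 3 | 0.1696 | 11 | 0.6865 | 11 | 0.6865 |
| 4 | 0.0694 | 12 | 0.4613 | 12 | 0.4613 |
| 5 | 0.0208 | 13 | 0.2361 | 13 | 0.2361 |
| 6 | 0.0047 | 14 | 0.0802 | 13 | 0.2361 |

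Counts of 7 or more on placebo add less than 0.0001.

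- Two-sided: 0.1464 + 0.2836 + 0.2444 + 0.1164 + 0.0320 + 0.0049 + 0.0004 = 0.828.
- One-sided: 0.1469 + 0.2954 + 0.2708 + 0.1164 + 0.0320 + 0.0049 + 0.0011 = 0.8675, or 86.8%.

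The type II error is therefore 1 - 0.828 = 17% or 1 - 0.868 = 13%. The claim is 12 or 8 percentage points too high.

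**Attempts to reproduce 95% (same rates, n and alpha).**

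| Method at 0.012 | Two-sided | One-sided |
|---|---|---|
| Fisher's exact | 82.8% | 86.8% |
| Fisher, mid-p | 86.8% | 92.0% |
| Uncorrected chi-square | 91.6% | - |
| Yates chi-square | 82.8% | - |
| Pooled normal approximation | 89.5% | 94.3% |
| Arcsine approximation | 90.1% | 93.8% |
| Unpooled normal approximation | 97.7% | 98.8% |

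Only two one-sided approximations come within 2 points of 95%, and neither is the named test. At nominal 0.05, Fisher gives 92.0% two-sided and 96.5% one-sided. Its attained size at a 12% null rate is then 0.0084 or 0.0158, so 0.012 is not recovered as an attained size either. With 15 per arm, exact power first reaches 95% at a nominal level of about 0.066 two-sided or 0.033 one-sided.

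**Does the choice of test in 11.2 matter?** The same enumeration on the 2x2 table (A+B against C-F) was used to find how often two tests disagree under 75% against 12%. Wherever uncorrected chi-square and two-sided Fisher differ, it is chi-square that rejects, so the disagreement is the difference in power:

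- At 0.012: 91.6% - 82.8% = 8.8%.
- At 0.05: 96.9% - 92.0% = 4.9%.
- With Yates correction: 0.0% at 0.012 and 0.01% at 0.05.

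Example: 9/15 against 2/15 gives p = 0.008 by uncorrected chi-square and p = 0.021 by two-sided Fisher. The maximum type I error at nominal 0.012 is 0.0161 for uncorrected chi-square and 0.0052 for Fisher.

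**Literal six-class reading.** This is a different test from the one that was sized. As an invented illustration, take counts A to F of 5, 6, 3, 1, 0, 0 against 1, 1, 4, 6, 2, 1. The A+B split is 11/15 against 2/15, with Fisher p = 0.0025; the unordered six-class chi-square gives p = 0.024. The two conflict at 0.012 but not at 0.05.

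**The case against.** The best case for the plan is that 11.1 and 11.2 are adjacent and should be read together. Section 11.1 supplies the A+B endpoint, names Fisher's test alone and gives 0.012. This largely stands. A reader might infer that 11.2 contradicts 11.1, or that the test and level are left to be picked after unblinding. The documents support neither: 11.2 says only that the arms are compared once the blind is broken, and three of the four missing items can be carried over. What remains is sidedness, which is stated nowhere, and the added chi-square option, which comes with no rule for choosing. That option is harmless if Yates correction is meant, but 11.2 does not say so.

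A second defence is that the design is still adequate, because two-sided Fisher at 0.05 has 92.0% power. This is correct, and it limits the consequence. It does not rescue the sentence: 0.05 appears nowhere in the documents, and 92.0% is not 95%.

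A third is that the figure may have a legitimate origin. The pilot rates quoted in 11.1 (52/66 and 2/30) give 95.7% two-sided at 0.012 with 15 per arm. A reader might instead link it to the ceiling of 40 subjects in section 3.1, since 20 per arm gives 94.98%. Nothing in the documents confirms either. Section 3.1 treats 40 as an enrolment limit for accruing 15 per arm, and 11.1 says the projection uses 75% and 12%. Neither origin makes the stated figure correct for the stated inputs.

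**Conclusion.** The power figure in 11.1 is wrong as written. For its own rates, sample size, test and alpha, exact power is 82.8% two-sided or 86.8% one-sided, against a claimed 95%. This rests only on the inputs in 11.1 and on independent binomial outcomes, and it holds for either sidedness.

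Section 11.2 is incompletely specified. On the inferred 2x2 table the test left open would change the conclusion in 8.8% of planned-effect trials at 0.012 or 4.9% at 0.05 if chi-square is uncorrected, and almost never if it is Yates-corrected. Most planned-effect trials would therefore reach the same conclusion either way.

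It does not follow that the trial is badly underpowered. The error lies in the stated pair of power and alpha. Both sections should be corrected before unblinding.

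**What to change.** **Section 11.1.** State whether the test is one-sided or two-sided, and confirm the level. If it is two-sided 0.012, restate power for 15 per arm as 82.8%. If the sponsor declares that the test level is two-sided 0.05, state 92.0% and replace 0.012.

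**Section 11.2.** Name a single primary test. Suggested wording: *The primary analysis is Fisher's exact test comparing the proportion in class A or B with the proportion in classes C to F between the two arms, at the alpha and sidedness given in section 11.1.* Delete chi-square from the sentence on the primary comparison.

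**Cost.** One corrected figure and a statement of sidedness in 11.1, and one or two sentences in 11.2. No new data, visits or subjects are needed. The downside is that the stated power becomes less favourable.

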5. METHODS AND STUDY PROCEDURES

The screening visit may take place up to 30 days prior to the first study visit, or may occur on the same day as the first study visit. After providing informed consent, subjects will provide a complete medical and neuro-otological history/exam and the study team would review their standard of care Ménière's work-up. Because subjects are typically established patients of the PI, the history may be obtained retrospectively from the subject's chart.

At the screening visit and at each subsequent visit, the subject will complete the ‘Meniere’s functional level scale’ question (Appendix B).

At the first study visit (which might be the same day as the screening visit) the study team will confirm eligibility and the subject will be randomized to either the oscillation or placebo group, with the study team blinded as to which treatment is received. The study team will be informed whether Device A or Device B are to be used (see 7.2). For treatment, the subject will be in a private room at the Department of Otolaryngology Clinton Woods Clinic. The designated treatment device (oscillator or placebo) will be placed over the mastoid of their involved ear and secured via an elastic/Velcro headband. The subject is positioned so as to place the endolymphatic duct into a gravitationally dependent orientation (the subject lying on their contralateral side with the face slightly tilted towards the floor). The device is turned on and operated for 30 minutes. The subject will be periodically monitored by study staff during this time. Following each treatment, patients will be evaluated for response and untoward side effects.

Study visits 2, 3 and 4 will be 7 days apart. Prior to treatment, a thorough review of the behavior of the subject’s Ménière's disease over the preceding week as well as any sequelae of their treatment will be recorded. A complete ENT and neuro-otologic exam will be completed.

Study visit 5 will be two weeks following the final treatment visit (visit 4). Subjects will have a complete medical and neuro-otologic exam and be observed for short-term results of the treatments.

The final study visit will be three months after study enrollment. Subjects will have a complete medical and neuro-otologic exam and be observed for longer-term results of the treatments. Specifically, the frequency and severity of any Ménière's disease attacks will be recorded and compared to pretreatment patterns.

Schedule of Activities

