Visit	0 (Screening)	1	2	3	4	5	6 (Final)
Visit Window	-30 days	0 days	7 days	14 days	21 days	35 days	90 days
Obtain informed consent	X	(X)					
Medical and otologic history	X	(X)					
ENT and neuro-otologic exam	X	(X)	X	X	X	X	X
Confirm eligibility/Randomize		X					
Document any recent vertigo		X	X	X	X	X	X
Meniere’s functional level scale (Appendix B)		X	X	X	X	X	X
Mastoid Oscillation/Placebo		X	X	X	X		
Document acute response		X	X	X	X		
Adverse event review		X	X	X	X	X	X

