5.2. Safety Assessments

As standard of care for evaluation and management of any Ménière's disease patient who has failed medical treatment and who is considering alternative forms of treatment, patients will provide information on their general medical and specific otologic health. They typically receive a thorough ENT and neuro-otologic physical exam per SOC. SOC audiologic testing is conducted if no previous testing in the 3 months prior to their visit is available. SOC ENG/VNG testing is not always necessary in the workup of the patient with Ménière's disease, but might be completed on a case by case basis per SOC. An MRI/MRA scan of the head would be completed on all patients per SOC to assure that there are no incidental tumors or aneurysms. Appropriate SOC screening lab tests would be completed to rule out metabolic, endocrine, inflammatory and autoimmune issues.

For safety assessment, the initial standard of care Ménière's workup described above will be documented when the subject enters the study. At each study visit after the first, subjects will be asked about changes to medical and otologic health, and in particular if they have had vertigo episodes since the last visit, and if so how frequent and of what duration. We will also ask if they experienced any discomfort related to the treatment and the subject will complete the 'Meniere's functional level scale' question (Appendix B).

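### Section 11.2 specifies no between-arm test for functional level and no baseline adjustment for any secondary outcome; adjusting would give a modest gain in precision at low to moderate correlation

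*Combined protocol and SAP*

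**What the plan says.** Section 11.2 (Planned Statistical Analysis) deals with the hearing outcomes in one sentence. It names hearing threshold and word recognition as secondary outcomes, "which will be compared by repeated-measures ANOVA". It does not say which visits enter the model, whether baseline is an outcome or a covariate, or whether the group-by-time interaction or the group main effect is to be read. The remaining secondary outcome is the patient's "functional level before and after treatment", with no test, no visit for the second value and no contrast between arms. The section does open with a general statement that the treatment and control arms will be compared once the blind is broken.

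On data collection, Section 5 states: "At the screening visit and at each subsequent visit, the subject will complete the" functional level question. The Schedule of Activities ticks that scale from Visit 1 to Visit 6 but not at screening. Section 5.2 mentions it in its account of visits after the first. For hearing, Section 5.2 says "SOC audiologic testing is conducted if no previous testing in the 3 months prior to their visit is available", and the Schedule of Activities has no audiometry row at any visit.

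On size, Section 3.1 says "We plan to enroll up to 40 subjects in order to accrue 15 randomized to the treatment arm" and the same number to control.

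**The concern.** A randomised trial with a baseline measurement can use it in several ways, and they differ in precision. Treating baseline as one more repeated outcome is usually not the best of them. The group-by-time test reduces to a comparison of change scores. The group main effect averages in a baseline taken before any treatment. With 15 per arm, precision on the secondary outcomes is scarce.

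For functional level the gap is more basic: the plan does not say how the arms will be compared. Subjects enter because their disease is active and uncontrolled (Sections 1.1 and 3.2), so some improvement through fluctuation and regression to the mean is to be expected in both arms. Section 2.2 gives the trial's purpose as showing whether improvement exceeds the natural history. A before-to-after change within one arm cannot show that; a between-arm contrast can. Both Visit 5 (day 35) and Visit 6 (day 90) come after the last treatment (day 21), so the plan also leaves open which visit counts as after.

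**Working it through.** **Inputs.** From the documents: 15 per arm, N = 30 (Sections 3.1 and 11.1), 1:1 allocation (Section 2.1). The documents give no power, SD, effect size or correlation for the secondary outcomes, so there is no planned figure to reproduce. Assumed: one baseline and one follow-up value, a continuous outcome with equal variance σ² at both times, and a baseline to follow-up correlation r of 0.3 to 0.95.

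**Variance of the between-arm estimate**, in units of 2σ²/n:

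- Change score (the same as the group-by-time test): 2(1 − r).
- ANCOVA: (1 − r²) × 27/26. The factor 27/26 is the average price of estimating the covariate slope at N = 30: 1/26 = 3.8% of variance.
- Group main effect with baseline counted as an outcome: the effect is averaged over one untreated and one treated time point, so it is half the follow-up effect. Rescaled to the follow-up effect, its variance is 2(1 + r).

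**Ratios.** ANCOVA to change = (1 − r²)/(2(1 − r)) × 27/26 = (1 + r)/2 × 27/26. ANCOVA to main effect = (1 − r)/2 × 27/26.

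| r (assumed) | ANCOVA / change | Equivalent extra subjects | ANCOVA / main effect |
|---|---|---|---|
| 0.5 | 0.75 × 27/26 = 0.779 | 1/0.779 − 1 = 28% | 0.26 |
| 0.7 | 0.85 × 27/26 = 0.883 | 1/0.883 − 1 = 13% | 0.16 |
| 0.9 | 0.95 × 27/26 = 0.987 | 1/0.987 − 1 = 1% | 0.05 |

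At r = 0.3 the ANCOVA to change ratio is 0.675. Simulation of 100,000 trials gave 0.672, 0.775, 0.881 and 0.985 at r = 0.3, 0.5, 0.7 and 0.9, in agreement with the formula.

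**Break-even against change.** (1 + r)/2 = 26/27 gives r = 25/27 = 0.926, or about 0.93. At r = 0.95 the ratio is 1.012, a loss of about 1%.

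**Illustrative power**, at an assumed standardised effect of 0.8 and two-sided alpha 0.05, change versus ANCOVA: 43% versus 58% (r = 0.3), 56% versus 67% (r = 0.5), 78% versus 83% (r = 0.7), 99.7% for both (r = 0.9).

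**Where the arithmetic applies.** It describes hearing threshold and word recognition if each has a baseline and a follow-up value, and the Schedule of Activities does not provide the follow-up value. Functional level is collected before and after treatment, but it has six ordered levels (Appendix 2) and is recorded at several visits, so these ratios do not carry over to it as figures.

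**Timing of the functional level baseline.** Section 5 starts it at screening, the Schedule of Activities starts it at Visit 1, and Section 5.2 speaks of visits after the first. No section says whether the Visit 1 value is taken before or after the first treatment.

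**The case against.** Under randomisation the group-by-time test is a valid, unbiased comparison of the arms, so the choice of ANCOVA over it is about efficiency and not correctness. That stands. Without r in the documents the gain cannot be fixed either, and it is negligible at high correlation. That also stands, and it limits the size of the point.

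Three stronger readings are tempting and are not supported.

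- A reader might infer that functional level will be tested within each arm. Section 11.2 does not say so, and its opening statement that the arms will be compared points the other way. What can be said is that no comparison is specified, which leaves a within-arm test possible.
- A reader might infer that the planned ANOVA halves the treatment effect. That holds only if the group main effect is read with baseline included as an outcome, and the plan names no contrast.
- A reader might take the large-sample ratio (1 + r)/2 and call adjustment free. At N = 30 it costs one degree of freedom and about 4% of variance.

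It can also be objected that a proportional-odds model with six categories and about 30 subjects risks sparse cells and an assumption that can hardly be checked. That is fair, and it favours a rank-based method as the default.

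**Conclusion.** The point holds in a limited form. Section 11.2 uses baseline as a covariate for no secondary outcome and names no test, visit or between-arm contrast for functional level.

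For a continuous outcome with one baseline and one follow-up value, baseline adjustment at 15 per arm would reduce variance against the group-by-time test by about 22%, 12% and 1% at assumed correlations of 0.5, 0.7 and 0.9, with nothing to gain above about 0.93. The advantage is much larger if the group main effect would otherwise be read.

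For functional level, whose data are scheduled, the benefit is a specified between-arm comparison; its gain in precision is not quantified here. For hearing, the benefit depends on follow-up audiometry that the schedule does not list. Only secondary outcomes are affected, and the primary analysis is untouched.

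**What to change.** In Section 11.2:

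- **Functional level.** Compare the arms at the final visit (Visit 6) by rank-based ANCOVA adjusting for the pre-treatment level, or by a proportional-odds model with the same covariate if the categories prove not too sparse. Do not rely on within-arm before/after change.
- **Hearing threshold and word recognition.** Replace the repeated-measures ANOVA with ANCOVA of the follow-up value on arm and baseline, wherever both audiograms exist. State that this depends on follow-up audiometry being collected.
- **Reporting.** Give each between-arm estimate with its 95% CI.

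Reconcile Section 5, the Schedule of Activities and Section 5.2 on when the functional level scale is first completed, so that the baseline is clearly a pre-treatment value.

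For functional level the cost is wording only, since the data are already scheduled. For hearing the wording alone is not enough: a follow-up audiogram has to be obtained. The statistical price is one degree of freedom (about 4% of variance) and possible sparse categories if the ordinal model is used. The change should be made before the blind is broken.
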